As described above, the current standard of care of catecholamine vasopressors is associated with significant, detrimental adverse effects associated with the mechanism of vasoconstriction of these agents. The reninangiotensin-aldosterone system (RAAS) is an essential hormonal regulator responsible for maintenance of BP via the actions of angiotensin II (AT2). In 2017, the FDA approved pharmacologic angiotensin II (Giapreza – Ang II) for patients with septic shock or distributive shock from other causes (Giapreza prescribing information). Distributive shock is defined as hypotension refractory to appropriate fluid resuscitation, which occurs frequently during the perioperative renal transplant period. After fluid resuscitation is unsuccessful, the use of catecholamine vasopressor agents are the mainstay of therapy for subsequent blood pressure support. As discussed, the narrow therapeutic window and significant risks associated with current vasopressor agents leave a crucial unmet medical need for safer and more effective therapies. In the ATHOS-3 Phase 3 clinical trial Ang II (Giapreza) was shown to have a more optimal pharmacodynamic profile compared to catecholamine vasopressors. It was found that Ang II (Giapreza) more frequently led to mean arterial pressure (MAP) goal attainment than the standard of care (i.e. norepinephrine) and the median duration of MAP goal attainment was 5 minutes for patients on Ang II (Giapreza); an effect that was sustained throughout the study period. Additionally, the usage of concurrent vasopressors was significantly decreased in subjects using Ang II (Giapreza) compared to the standard of care. Lastly, it was found that Ang II (Giapreza) was a safe medication with the most common ADE (> 4% and > 1.5 x placebo) being: thromboembolic events, thrombocytopenia, tachycardia, fungal infection, delirium, acidosis, hyperglycemia, and peripheral ischemia. Despite the commonality of distributive shock in the intraoperative and postoperative period of renal transplants, there are no data available evaluating Ang II (Giapreza) in this population. The more balanced vasoconstriction of AT2 within the kidney vasculature yields a net result of increased filtration fraction and can preserve kidney function (Fehrer 2012). This has been confirmed with animal and clinical human investigations in patients with the highest known risk of developing acute kidney injury (AKI): septic shock (Lankadeva 2018, Tumlin 2018). Thus, it is hypothesized that the use of Ang II (Giapreza) in the intraoperative and perioperative period for renal transplant patients may lead to improved BP management and more optimal safety outcomes compared to the current standard of care conventional catecholamine vasopressors. Therefore, the purpose of this study is to evaluate the safety and efficacy of Ang II (Giapreza) in improving hypoperfusion among renal transplant patients during the critical peri-op period.

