
The following section is designed to describe the current peri-op processes of renal transplant patients at UI Health in order to clearly delineate how this specific research protocol will deviate from the standard of care.

The normal care process for deceased donor kidney transplants (DDKT) at University of Illinois Hospital and Health Sciences (UIHHSS) includes the following:

PRE-TRANSPLANT

- Patient is end-stage renal disease (ESRD) on dialysis meeting set criteria for kidney transplant
- Patient obtains medical and social clearance for kidney transplant including blood tests (SCr, LFTs, Thyroid studies, CBC w/ diff); Diagnostics: chest X-ray; Cardiac clearance: ECHO, ECG, +/- Stress test, +/- Left heart cath; Cancer screening: colonoscopy, skin CA screening, prostate exam (if applicable), gynecological exam (if applicable); pregnancy screening (if applicable); Surgical clearance; and Nephrology clearance
- Once cleared, patient is listed with our institution and placed on our waitlist
- Patient has yearly check-in visits to re-evaluate if still eligible for transplant and medically able to obtain transplant
- If kidney becomes available, patient is notified to urgently come to either the UIHHSS Surgicenter or Emergency Room to be expeditiously admitted to the OR for their transplant (this time is generally limited to 1-3 hours)
 - It should be noted that time is of extreme value as longer time that passes before implantation of donor kidney has been associated with worse renal outcomes in recipient

DURING TRANSPLANT

- The transplant operation begins.
- If intraoperative hypotension occurs (e.g. SBP < 120 mmHg) the attending surgeon and attending anesthesiologist will:
 - Give blood products first if patient bleeding
 - If not bleeding or hypotensive despite blood products, intravenous fluids will be given
 - If hypotensive despite intravenous fluids then the attending surgeon and attending anesthesiologist will assess for cardiogenic shock and if suspected give inotropes
 - If not in cardiogenic shock and hypotensive despite fluids (+/- inotropes) then catecholamine vasopressors will be given for the treatment of distributive shock.
 - Vasopressor medications will be titrated intraoperatively to achieve goal BP

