4.2 Exclusion Criteria

- Pregnant patients (they would be excluded from receiving a transplant)
- Prisoners
- History of mesenteric ischemia
- History of aortic dissection
- History of abdominal aortic aneurysm

AT2 in Kidney Transplant
Page 8 of 22
Version 2.1
6-1-20

- Allergy to mannitol
- Absolute neutrophil count < 1000 cell/mm3 (within past 18 months)
- Diagnosis of Raynaud's phenomenon, systemic sclerosis or vasospastic disease

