The study drug will be provided by La Jolla Pharmaceuticals for this study but they are not the study sponsor or providing any other financial support. Drug distribution will be managed by the Investigation Drug Service (IDS) at UI Health who has the capacity to retain all of the study drug in appropriate temperature-controlled settings. IDS will be used as this is a novel medication, not yet on formulary at UIHHSS, and this is a research investigation. They will maintain and dispense the medication for each kidney transplant in which subjects have consented in the event that vasopressors are required. Additionally, the medication will be ordered via Cerner/EPIC as a study medication and will be programmed into the Alaris pumps to be dosed via the dosing protocol listed above. Ang II (Giapreza) will not be used outside of the study protocol at our institution and will only be available under the electronic study order. Verifying pharmacists will be in-serviced regarding the study protocol and will be aware that this medication is only available and should be dispensed under the study order and as such not used in other contexts.

FOR STUDIES THAT COLLECT EXISTING OR PROSPECTIVE DATA

Health and laboratory data will be extracted manually from the electronic medical records (i.e. Cerner or Epic) for both arms of the study. Data will be prospectively captured over the course of 3 months after study initiation (i.e. using Ang II (Giapreza) for vasopressor management during kidney transplant) for the pilot. The data will be collected and input into a Redcap database for analysis. Data analysis will be performed using Spss.v25 computer software. Data collection will include the variables below.

Baseline characteristics:

-Age (years of age at the time of transplant)

- -Gender (M/F)
- -Race
- A) White
- B) Black
- C) Asian
- D) Hispanic
- E) Other
- -Weight (kilograms at time of transplant)
- -Height (centimeters at time of transplant)
- -Body mass index (kg/m² at time of transplant)
- -Duration of time on hemodialysis (years)
- -Donor baseline serum creatinine (mg/dL)
- -Warm/cold ischemia time (hours)
- -KDPI
- -Baseline systolic/diastolic/mean arterial pressure (mmHg)
- -Baseline heart rate (HR)
- -Comorbidities
- A) Hypertension
- B) Hyperlipidemia
- C) Heart failure with preserved ejection fraction
- D) Arrhythmias
 - -Atrial fibrillation
 - -Other
- E) Peripheral vascular disease
- F) Coronary artery disease
- G) Pulmonary hypertension
- H) Diabetes

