- -Induction immunosuppression regimen
- -Maintenance immunosuppression regimen
- -First SCr, CrCl, calculated GFR after operating room (mg/dL)
- -Daily SCr, CrCl, calculated GFR after operating room (mg/dL)
- -Average SCr, CrCl, calculated GFR during hospitalization (mg/dL)
- -First serum lactate after operating room (mmol/L)
- -Peak serum lactate after operating room (mmol/L)
- -Duration of elevated (> 2 mmol/L) lactate after operating room (mmol/L)
- -Discharge SCr, CrCl, calculated GFR from hospital (mg/dL)

- -1-month SCr, CrCl, calculated GFR, 3-month SCr, CrCl, calculated GFR
- -Postoperative diuretic utilization (total milligrams of furosemide equivalents)
- -Postoperative midodrine usage (total milligram during hospitalization), duration of usage (days), used upon discharge (Y/N)
- -Postoperative mannitol utilization (Y/N)
- -Baseline serum albumin (mg/dL)
- -Need for renal replacement therapy in the first year after transplantation (Y/N)
- -Mortality during hospital admission for kidney transplant
- -Presumed or definitive allograft rejection rate during hospital admission for kidney transplant
- -Biopsy needed to rule out rejection (Y/N)
- -Calcineurin inhibitor (in tacrolimus equivalents) serum level at 1 week, 1-month, 3-month, 6-month
- -Suspicion for other types of shock (e.g. sepsis, cardiogenic, hemorrhagic as noted in chart documentation)

Safety data points:

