Patients will be monitored according to standard monitoring for patients in the peri-operative transplant and collection of ADE will focus on those found in clinical studies using Ang II (Giapreza). The safety endpoints that will be captured will include: incidence of intraoperative arrhythmias for those who receive study drug intraoperatively (confirmed via EKG, flowsheet, or note documentation), incidence of postoperative arrhythmias occurring while receiving study drug postoperatively (confirmed via EKG, flowsheet, or note documentation), incidence of digital or other peripheral/visceral ischemia occurring during hospitalization for kidney transplant (as noted in chart documentation), incidence of venous or arterial thrombosis occurring during the hospitalization for kidney transplant (captured by ultrasound or other diagnostic imaging), incidence of thrombocytopenia while receiving study drug (as defined as platelet count < 50,000), incidence of post-operative fungal infections prior to discharge (as documented by the clinical care team), incidence of delirium while receiving study drug (as documented by the clinical care team), incidence of insulin infusion utilization while receiving study drug, pH values in the ICU at 24hrs, 48hrs, and 72hrs (if available). All of the noted safety variables above are routinely monitored for as part of ICU care.

Data Management

All patients that provide informed consent and receive Ang II (Giapreza) will have their data extracted. These patients will be considered included and associated with an alpha-numeric code that is linked to their medical record number (MRN). This list will be kept in a password protected Excel file on the primary investigator's computer stored on the H drive behind the University firewall on the primary investigator's password protected computer in a locked office. It will be available only to the co-investigators. Lastly, all data collected will not contain PHI and will be stored in Redcap.

All patients that provide informed consent but DO NOT receive Ang II (Giapreza) will be considered a screening failure and NO data will be extracted and they will not be associated with an alpha-numeric code linked to their MRN.

Records retention:

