Probably Related: An event that follows a reasonable temporal sequence from administration of the Ang II and there is a biologically plausible mechanism for Ang II (Giapreza) to cause or contribute to the AE and the event could not be reasonably explained by the known characteristics of the participant's clinical state.

For reporting purposes, both 'Possibly Related' and 'Probably Related' will be considered **Related**.

Adverse events will also be graded by severity according to CTCAE criteria.

- -Grade 1: Mild; Asymptomatic or mild symptoms; clinical or diagnostic observations only; intervention not indicated.
- -Grade 2: Moderate; Minimal, local or noninvasive intervention indicated; limiting age-appropriate instrumental activities of daily living.
- -Grade 3: Severe; Medically significant but not immediately life-threatening; hospitalization or prolongation of hospitalization indicated; disabling; limiting self-care activities of daily living.
- -Grade 4: Life-threatening consequences; urgent intervention indicated.
- -Grade 5: Death related to AE.

Given this is a clinical trial a Data Safety Monitoring Board (DSMB) will be established. This board will be composed of two Critical Care Pharmacists ([name] and [name]) with intimate knowledge of Ang II (Giapreza), vasopressors, Ang II (Giapreza) safety endpoints and no relationship to the conduct of the trial. This DSMB will review the safety endpoints collected above after 5, 10, 15, and 20 subjects are enrolled. They will be provided a Safety Summary Report for the allotted number of patients with "Relatedness" and Grading of captured ADE as described above.

Study Halting Criteria: For existing participants study drug will halt dosing immediately until further safety analysis and assessment by the DSMB can be completed and no further enrollment will take place until approved by the DSMB. The halting criteria are as follows:

- Two participants experience the same Grade 4 adverse event considered related to study drug
- 20% of the participants at time of analysis experience the same Grade 3 adverse event
- One participant experiences a Grade 5 AE considered related to study drug

Study can be restarted if the DSMB says it is okay to continue.

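### Thrombocytopenia is recorded only as a count below 50,000 on drug, with no pre-drug or lowest platelet count listed, so large falls and pre-existing low counts cannot be identified

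*Combined protocol and SAP*

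**What the plan says.** Section 6.0 (Safety data points) lists "incidence of thrombocytopenia while receiving study drug (as defined as platelet count < 50,000", and Section 11.0 repeats it. There is no unit, no new-onset condition and no reference to a pre-drug value.

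Thrombocytopenia is one of the eight common adverse events that Section 2 carries over from the registrational trial: "thromboembolic events, thrombocytopenia, tachycardia, fungal infection, delirium, acidosis, hyperglycemia, and peripheral ischemia". Section 3.0 rests the safety objective on the incidence of such events.

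The data lists in Section 6.0 give baseline or extreme values for other measures, for example "Baseline systolic/diastolic/mean arterial pressure (mmHg", "Baseline serum albumin (mg/dL" and "Peak serum lactate after operating room (mmol/L". pH is taken as a numeric value at 24, 48 and 72 hours in the same sentence as the platelet cut-off. No platelet count is listed.

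The only blood-count exclusion in Section 4.2 is "Absolute neutrophil count < 1000 cell/mm3 (within past 18 months". Pre-transplant clearance in Section 2 includes "blood tests (SCr, LFTs, Thyroid studies, CBC w/ diff", and Section 6.0 says the safety variables are monitored routinely in ICU care.

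Section 11.0 adds a relatedness assessment and states: "Adverse events will also be graded by severity according to CTCAE criteria". The DSMB receives the captured events with relatedness and grade after 5, 10, 15 and 20 subjects.

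**The concern.** A platelet count is a number, and the plan reduces it to yes or no at one cut-off without keeping the number. Two kinds of information are then lost.

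- A patient whose count falls steeply but stops at or above 50,000 is a non-case, indistinguishable in the listed data from a patient whose count never moved.
- A patient whose count was below 50,000 before the first dose meets the written definition on drug, and no listed item shows that the low count came first.

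At stake is the description of one of eight named safety events in a study with 20 treated patients. The design describes one treated group, so a patient's own pre-drug count is the only within-study reference for whether a low count is new. The DSMB is affected too: it sees captured events, and a large fall above the cut-off is not one.

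**Working it through.** The plan gives no expected rate for this endpoint, and Section 12.0 states that no sample size calculation was made, so there is no figure to reproduce. The check compares the definition with the data lists and then applies it to example values.

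**Step 1: is a platelet value listed anywhere?** In Section 6.0, the baseline, intraoperative, postoperative hemodynamic and postoperative clinical lists contain none. The safety list has only the cut-off. Section 4 sets no platelet floor for entry.

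**Step 2: apply the rule as written.** All counts below are assumed, in thousands. Percentage fall = (pre-drug − lowest) / pre-drug.

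| Pre-drug | Lowest on drug | Fall | Scored as |
|---|---|---|---|
| 250 | 55 | 195/250 = 78% | no event |
| 250 | 60 | 190/250 = 76% | no event |
| 300 | 50 | 250/300 = 83% | no event |
| 52 | 48 | 4/52 = 8% | event |
| 45 | 45 | 0% | event, unless read as new onset only |

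**Step 3: weight of one patient.** With 20 treated patients (Section 5.0), one patient moves the incidence by 1/20 = 5 percentage points.

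**Step 4: how likely is a pre-existing low count?** The documents give no share p of recipients who start below 50,000. Over an assumed range, the chance of at least one among 20 is 1 − (1 − p)^20:

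| Assumed p | Expected number, 20p | Chance of at least one in 20 |
|---|---|---|
| 1% | 0.2 | 18% |
| 2% | 0.4 | 33% |
| 5% | 1.0 | 64% |
| 10% | 2.0 | 88% |

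The true share may lie at or below the bottom of this range, since recipients pass a blood count and several clearances before listing. The missed large fall is therefore the likelier practical loss.

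**Step 5: what would the two added values change?** The 250-to-55 patient stays a non-case, but the 78% fall is reported. The 52-to-48 patient stays a case, now shown as an 8% fall. The 45-to-45 patient moves to a separate list.

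**The case against.** The strongest reply has four parts.

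- **Incidence ordinarily means new events, and the relatedness step can mark a pre-existing low count as not related.** This partly stands: the plan does not direct that such patients be counted. But the definition does not exclude them, a relatedness label does not remove a patient from the count, and no listed item holds the pre-drug value needed for either judgement. Neither argument reaches the missed falls.
- **The lists may not be exhaustive, and someone must read the counts to apply the cut-off.** True, and the REDCap form is not among the documents. The plan still does not require the number to be kept.
- **The study is a convenience-sample pilot that only counts adverse events.** This limits how much should be asked. Two chart values are in proportion.
- **The added summary leaves the endpoint's threshold as it is.** Correct. The summary shows what the threshold hides and does not replace it.

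A reader might also infer four stronger things that the documents do not support.

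- **That the endpoint can show no platelet effect at all.** New falls below 50,000 would still be captured.
- **That change from baseline would show an effect of Ang II without a comparator.** Under Section 6.0 the drug starts during or after surgery, after fluids and, if the patient is bleeding, blood products. Induction immunosuppression is given as well. A before-after change mixes all of these with the drug.
- **That severity grading is impossible.** Section 11.0 describes grades by clinical consequence, and investigators can assign them from the chart without using the yes/no field.
- **That a pre-existing low count would trip the Grade 3 halting criterion at the first DSMB look, where 20% of 5 is one patient.** This needs a Grade 3 assignment, and the documents tie no platelet value to that grade.

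**Conclusion.** The point holds as a gap in what is recorded for a stated safety endpoint. The written rule scores any fall that stops at or above 50,000 as no event, whatever its size, and the listed data cannot separate a new low count from an existing one. Both follow from the text alone.

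The size is modest. One patient is worth 5 percentage points of incidence. The 78% fall is an assumed example, and the frequency of pre-existing low counts is unknown and may be small. The conclusion assumes that the data lists reflect what will be extracted. It makes no claim about whether Ang II affects platelets. The change should be made because it is cheap and the safety description is poorer without it.

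**What to change.** In Section 6.0, and in the matching text of Section 11.0:

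1. Add two numeric data items: the last platelet count before the first Ang II dose, with its date and time, and the lowest count in the endpoint window.
2. Keep the 50,000 cut-off and state its unit. Count as incident only patients at or above 50,000 before drug, and give that number as the denominator.
3. List patients already below 50,000 before drug separately, with both counts.
4. Report individual and median percentage change as a descriptive safety summary, and include it in the DSMB report.
5. State that the change cannot be attributed to Ang II without a comparator, because surgery, fluids, blood products and induction also affect platelets.

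The cost is two chart values per patient, at most 2 × 20 = 40 values. No new tests should be needed, since blood counts belong to routine care. The drawback is that for intraoperative starts the pre-drug count may predate surgery. Recording its date and time makes that visible but does not remove it.

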3.0 OBJECTIVES/AIMS

Study Objectives

Primary: To evaluate the hemodynamic effectiveness of Ang II (Giapreza) for intraoperative and postoperative hypotension in kidney transplant patients. This will be evaluated by the time to reaching BP goal.

Secondary: To evaluate the safety of Ang II (Giapreza) for intraoperative and postoperative hypotension in kidney transplant patients. This will be evaluated by collecting the incidence of common adverse events (ADE) seen from other Ang II (Giapreza) studies in this patient population.

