- -Type I
- -Type II

Intraoperative Hemodynamic Data Points:

- -Intraoperative BP (SBP, DBP, MAP) every 5 minutes
- -Intraoperative heart rate every 5 minutes
- -Maximum dose of Ang II (Giapreza) (ng/kg/min)
- -Duration of Ang II (Giapreza) (hours)
- -Number of intraoperative vasopressors (if applicable)
- -Intraoperative agents used in addition to Ang II (Giapreza) (if applicable)
- -Dopamine (Y/N)
- -Norepinephrine (Y/N)
- -Epinephrine (Y/N)
- -Phenylephrine (Y/N)
- -Vasopressin (Y/N)
- -Minimum intraoperative SBP and DBP (mmHg)
- -Minimum intraoperative HR (bpm)

- -Intraoperative volume resuscitation (L)
- -Type of crystalloid and volume: 0.9% NaCl, PlasmaLyte, Lactated Ringers (L)
- -Type of colloids and volume: Albumin, Hydroxyethyl Starch, Mannitol (L)
- -Intraoperative blood product utilization (volume and type of blood products administered)

Post-operative Hemodynamic Data Points:

- -Postoperative BP (SBP, DBP, MAP mmHg) every 1 hour for the first 72 hours or duration of vasopressors (whichever is longer) after transplant
- -Postoperative HR (bpm) every 1 hour for first 72 hours or duration of vasopressors (whichever is longer) after transplant
- -Maximum dose of postoperative Ang II (Giapreza) ng/kg/min
- -Maximum dose of postoperative other vasopressors (in norepinephrine equivalents if applicable)
- -Starting dose of postoperative Ang II (Giapreza) and other vasopressors (in norepinephrine equivalents if applicable)
- -Duration of postoperative vasopressors (hours if applicable)
- -Number of postoperative vasopressors (if applicable)
- -Minimum postoperative BP (SBP, DBP, MAP mmHg) in first 72 hours after transplant (in first 24hrs, second 24hrs, third 24 hrs, and total 72hrs)
- -Minimum postoperative HR (bpm) in first 72 hours after transplant (in first 24hrs, second 24hrs, third 24 hrs, and total 72hrs)
- -Maximum postoperative BP (SBP, DBP, MAP mmHg) in first 72 hours after transplant
- -Maximum postoperative HR (bpm) in first 72 hours after transplant
- -Postoperative agents used:
- -Dopamine
- -Norepinephrine
- -Epinephrine
- -Phenylephrine
- -Vasopressin
- -Postoperative volume resuscitation (L in the first 24hrs, 48hrs, 72hrs)
- -Daily intake volume (milliliters) during ICU admission
- -Daily urine output volume (milliliters) during ICU admission
- -Postoperative blood product utilization (volume and type of blood products administered during ICU admission after operating room)

Post-operative Clinical Data Points:

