7.0 EXPECTED RISKS/BENEFITS

The main anticipated benefit is the potential to establish improved hypotension management of future kidney transplant recipients at UIHHSS. This study could also potentially lead to further outcome studies on the effect vasopressors have on post-operative kidney transplant patients or studies directly comparing individual agents. Conversely, the expected risks are low given the existing data in critically ill patients with septic or other distributive shock. In the ATHOS-3 trial patients, the majority of patients evaluated were septic shock patients with a far greater severity of illness than kidney transplant recipients. In that investigation, there were no lifethreatening ADE's and minimal that were greater than placebo: most common ADE (> 4% and > 1.5 x placebo) being: thromboembolic events, thrombocytopenia, tachycardia, fungal infection, delirium, acidosis, hyperglycemia, and peripheral ischemia. With all medications, there are risks of adverse reactions. All adverse reactions that occur at an incidence of greater than 4% (and > 1.5 x placebo) in the prescribing information will be discussed individually with the subject prior to informed consent. These data points will be collected as noted above in the data collection section. There is also the risk of poorer outcomes and overall health with this agent. As with all investigations, there is a risk of breach of PHI. However, this risk is very low due to the numerous safeguards in place as described above and from using data collection in Redcap. Additionally, password protection and the hospital firewall security further reduce the likelihood of breach of information.

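### Hyperglycemia and acidosis, two of the eight adverse events the protocol names, cannot be validly reported as incidences from the listed data

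*Combined protocol and SAP*

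**What the plan says.** Section 3.0 states that safety will be judged by "collecting the incidence of common adverse events (ADE) seen from other Ang II (Giapreza) studies in this patient population". Section 2 (Need for the Study) lists the common events as "thromboembolic events, thrombocytopenia, tachycardia, fungal infection, delirium, acidosis, hyperglycemia, and peripheral ischemia", and section 7.0 repeats the same eight. Section 7.0 then says "These data points will be collected as noted above in the data collection section".

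The safety data points in 6.0, repeated in 11.0, give a named incidence for thrombosis, thrombocytopenia (with a platelet cut-off and an on-drug window), fungal infection, delirium, ischemia and arrhythmias. For glucose disturbance and acid-base status the only safety items are "incidence of insulin infusion utilization while receiving study drug, pH values in the ICU at 24hrs, 48hrs, and 72hrs (if available").

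**The concern.** The objective calls for incidences, and 7.0 refers the reader to the data list for them. For two of the named events the list does not hold what an incidence needs.

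- **Hyperglycemia.** An insulin infusion is a treatment decision. Counting it misses high glucose managed in any other way. It also counts an infusion that was already running when Ang II started, and diabetes is one of the comorbidities to be recorded.
- **Acidosis.** Raw pH at fixed ICU times is not an event. No cut-off turns a value into a case, no pre-drug value separates new from existing acidosis, and nothing ties a reading to the infusion.

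At stake is a safety report that appears to cover the known profile, but gives an insulin-use rate in place of hyperglycemia and uninterpretable pH values in place of acidosis. The monitoring board is affected too. Section 11.0 sends it the captured events with relatedness and severity grade, and neither an insulin-infusion flag nor a bare pH value is an event that can be graded.

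**Working it through.** **1. Denominator.** Section 5.0 plans for 20 treated patients from 40 consented, and 13.1 assumes that about 50% need vasopressors: 20 / 0.50 = 40, so the plan's figure is reproduced. Patients who consent but are not treated contribute no data (6.0, Data Management). Any incidence therefore has a denominator of at most 20.

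**2. Matching the eight named events to the data list (6.0 and 11.0).**

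| Named event | What is listed | Incidence obtainable? |
|---|---|---|
| Thromboembolic events | Incidence of thrombosis on imaging | Yes |
| Thrombocytopenia | Incidence, platelets below 50,000, on drug | Yes |
| Fungal infection | Incidence before discharge | Yes |
| Delirium | Incidence on drug | Yes |
| Peripheral ischemia | Incidence during the admission | Yes |
| Tachycardia | Arrhythmia incidence; serial heart rate | Yes, once a threshold and window are set |
| Hyperglycemia | Insulin infusion on drug; no glucose | No |
| Acidosis | Up to three ICU pH values; no cut-off | Not validly |

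Five of the eight have a direct endpoint, one is derivable, and two are not validly obtainable: 2 / 8 = 25%.

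**3. Hyperglycemia: possible size of the undercount.** The documents give no rates, so these are assumptions. Suppose 20% to 40% of 20 patients have hyperglycemia, and 10% to 50% of those receive an infusion.

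- True cases: 20 × 0.20 = 4 to 20 × 0.40 = 8.
- Cases counted: 4 × 0.10 = 0.4 to 8 × 0.50 = 4.
- Reported incidence: 0.4 / 20 = 2% to 4 / 20 = 20%, against a true 20% to 40%.

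Infusions begun before Ang II push the count the other way, by an amount the documents do not allow one to estimate.

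**4. Acidosis: timing.** Section 2 describes the recipients as having end-stage renal disease and being on dialysis, so a low pH may precede the drug. Section 6.0 allows Ang II to be weaned during surgery. For such a patient every listed pH is taken in the ICU after exposure has ended. A patient whose infusion runs on in the ICU may have an on-drug reading, but the plan does not require one.

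**5. What a repaired incidence could say.** Exact (Clopper-Pearson) 95% intervals:

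- 0/20: 0 to 16.8%
- 1/20: 0.1 to 24.9%
- 4/20: 5.7 to 43.7%
- Zero events with pH available in only 15 or 10 patients (assumed): upper limit 21.8% or 30.8%

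**6. Link to halting.** One criterion in 11.0 is 20% of participants with the same Grade 3 event. At the planned reviews this is 0.20 × 5 = 1, 0.20 × 10 = 2, 0.20 × 15 = 3 and 0.20 × 20 = 4 patients. With counts this small, one or two uncaptured Grade 3 events could decide whether the criterion is met.

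**The case against.** The strongest reply is that the safety list is not worded as exhaustive. Section 11.0 adds relatedness, CTCAE grading and board review, so a clinically evident episode of hyperglycemia or acidosis could still be recorded. Diabetes type is recorded, and the relatedness definitions would let an infusion that began before Ang II be judged unrelated. Post-operative lactate (initial, peak and duration of elevation) gives further metabolic information, and a pH cut-off could be applied at analysis. With 20 patients and one treatment, estimates stay imprecise and attribution stays weak whatever definitions are used.

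Part of this stands. The data on acidosis are partial rather than absent, sharper definitions will not narrow the intervals in step 5, and a pre-drug value does not establish cause. However, an open-ended list commits no one to extracting glucose or on-drug pH. Lactate does not define acidosis and is also collected only after surgery. A cut-off chosen later cannot supply a baseline, and choosing it after the results are known invites selective definition.

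A reader might also infer that tachycardia belongs with these two, so that three of the eight events go unreported. The documents do not support that. Although "Minimum intraoperative HR (bpm") is the only intraoperative heart-rate summary, 6.0 collects heart rate every 5 minutes in surgery and hourly for at least 72 hours afterwards, with the postoperative maximum. The intraoperative maximum follows from the series, and arrhythmia incidence may cover some cases. Only a threshold and an on-drug window are missing.

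**Conclusion.** The point holds for two of the eight named events. Hyperglycemia incidence cannot be recovered from the planned dataset, because no glucose value is in it. An acidosis count could be made where pH exists, but it could not be separated from pre-existing acidosis or reliably placed within exposure. Tachycardia needs only a minor clarification. It would go too far to say that the safety objective as a whole cannot be answered: five events have direct endpoints and a sixth is derivable.

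The count of two rests on the data list in 6.0 being what is extracted. The size of the hyperglycemia undercount rests entirely on the assumed rates in step 3 and shows only a plausible range. The primary hemodynamic objective is unaffected. This is a cheap improvement to a stated secondary objective, best made before extraction begins.

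**What to change.** Amend the safety data points in 6.0 and the matching text in 11.0:

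- **Hyperglycemia.** Extract the last charted glucose before Ang II and all charted values during it. Report incidence against a cut-off fixed before data review. Keep insulin infusion as a descriptor, flagged if it began before Ang II.
- **Acidosis.** Extract the last pH before Ang II and all charted pH values during the infusion, in addition to the 24, 48 and 72 hour values. Report new or worsened acidosis against a cut-off fixed in advance.
- **Tachycardia.** State a heart-rate threshold and an on-drug window, to be applied to the readings already collected.
- **Reporting.** Give the number of patients with data as the denominator for each event, with an exact confidence interval.

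The cost is data-dictionary wording and some extra chart extraction, with no new tests. The downside is that glucose and pH drawn only when clinically indicated will be missing for some patients, and perhaps not at random, so the denominators will be incomplete and must be shown.
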